## 10 DATA COLLECTION, SITE MONITORING, AND ADVERSE EXPERIENCE REPORTING

### 10.1 Records to Be Kept

**Records Retention.** Participation in this study requires that original study documents be retained for a minimum of 2 years following notification of the FDA by the study CCC that investigations have been discontinued. This standard complies with U.S. FDA regulations (21 CFR §312.62[c]). Records must not be destroyed without first contacting the CCC to ensure that the time limits defined in the regulations have been met. Study centers in countries other than the US participating in the trial may have to comply with different requirements but should comply with whichever requirement is longer.

For the purposes of this section, “original study documents” are defined as:

- Subject medical records created at or available to the enrolling center during the subject’s participation in the trial, or any other document that supports entries in the EDC system and represents the original source of that information, including but not limited to applicable sections of medical charts, patient correspondence, laboratory data, pharmacy logs and drug accountability forms, as well as any forms or documents used to compile or maintain original subject data or study procedural information. Intermediary documents and worksheets used to organize and compile original records into a form that facilitates easier transcription into the EDC do not represent original study documents. Certain data may be entered

directly into the EDC in which case the EDC system represents the original study document.

- All Essential Regulatory Documents (as defined under Good Clinical Practice Regulations) including: all material communications with the IRB; all communications with the Sponsor (including the surgical center, reading center, outcomes committee, endpoint committee, safety monitor, Emissary's monitoring staff, etc.) that are related to study subjects or which otherwise document material study-related procedures or safety issues; and, all training records and documentation that all participating staff are suitably qualified and authorized (CVs, 1572, Delegation Log, etc.).
- Archival copies of the data and electronic documents from the VISION-EDC system.

All study documents should be uploaded to the Electronic Trial Master File (eTMF) section of the VISION-EDC system. VISION will be used as the master repository for all site and Sponsor regulatory documents, and all patient source documents with the exception of DICOMs and any records not uploaded to the EDC (perhaps for confidentiality reasons or do to specific site discretion, such as might be suitable for financial contracts), sites generally do not need to maintain duplicate local files unless otherwise mandated by local institutional requirements.

At the conclusion of the study, all entered patient data and uploaded documents (with the exception of Modified Rankin videos and DICOMs) in the VISION-EDC system will be archived and provided to the site on DVDs. Modified Rankin video interviews uploaded to the Glasgow outcomes center will be destroyed at the conclusion of the trial in accordance with informed consent commitments. Due to their extreme size, DICOMs submitted to the EDC system will not be maintained long-term in the EDC system, but rather will be promptly deleted once they have been reviewed by the reading and surgical centers. Sites will be responsible for retaining DICOMs via their local PACS system (or local copies of CDs).

Regulations require that study documents (including the archive CDs and any study documents not uploaded to the EDC) must be retained in the files of the responsible investigator for potential review by regulatory agencies. As this is an international study conducted under the jurisdiction of multiple regulatory bodies (FDA, NIH, Health Canada, ICH, etc.) and for not in support of any one specific regulatory application, retention requirements may be considerably longer than what may be required under local or regional regulations or other trials being conducted at the site. As such, the principal investigator must retain the study documents until otherwise instructed by the coordinating center. The expected retention period is a minimum of 2 years after the final report is submitted to the FDA after the conclusion of the overall clinical trial, irrespective of any particular site's participation.

## 10.2 Role of Data Management

10.2.1 Investigator/Institution will permit trial-related monitoring, audits, IRB/IEC review, and regulatory inspections by providing direct access to source data and documents.

**Data Collection and Reporting:** Data for each patient will be reported and recorded on electronic case report forms. Electronic case report forms (eCRF) must be completed for every randomized patient. This means all patients who have a signed informed consent, undergo screening procedures, and fulfill all eligibility criteria.

The electronic CRF (eCRF) will be completed by the site investigator(s) listed on the Form FDA 1572 or otherwise designated by the site Principal Investigator. If any entry on a source document requires change, a single line will be drawn throughout the incorrect entry, and the correction will be entered in ink, initialed and dated. Whiteout, erasures, or obliteration on source data are not permitted.

10.2.2 **Statistical Center responsibilities as the Data Coordination Center (DCC).** The responsibilities of the DCC in the MISTIE III trial include: trial design development and monitoring of trial performance, data management planning, review and verification of CCC data for analysis/presentation, statistical design and analysis, and reporting of results for various aspects of trial management (e.g., safety, site performance, surgical performance, fidelity of adaptive randomization) and trial evaluation (e.g., DSMB reporting, interim analyses, publications, resource sharing). The DCC will collaborate closely with CCC throughout the duration of the trial, and will rely on CCC leadership to provide the appropriate scientific and clinical guidance to ensure the successful completion of the responsibilities described above.

## 10.3 Quality Assurance

MISTIE III will have a robust safety and data monitoring program in full compliance with NIH policy of 10-Jun-1998 as expanded by NINDS guidelines published 14-Sep-2011 in addition to compliance with all applicable U.S. and international GCP regulations. This program, designed to safeguard the well-being of study participants and to ensure scientific integrity, will include the following components:

- A NINDS-appointed independent DSMB;
- A dedicated safety committee comprised of two independent medical monitors (a neurologist and a neurointerventionalist/neurosurgeon) with a dedicated independent safety compliance officer;
- Oversight of the CCC and the multicenter trial by an independent IRB in addition to the individual site IRBs;

- A surgical committee with a dedicated surgical center providing oversight during patient enrollment;
- An outcomes committee composed of an independent monitor to review the integrity of the multiple outcome assessments and a centralized, dedicated Glasgow outcomes center providing standardized adjudication of mRS assessments;
- An imaging reading center providing independent assessment of clot resolution, edema, and mass effect;
- Automated data quality checks at the time of EDC form completion by the investigational site;
- Dedicated independent data monitoring and QA teams (Emissary International and The George Institute);
- A robust training program prior to site activation, interactively during each medical and surgical enrollment, and with monthly advanced training topics, monthly newsletters, and quarterly performance reviews.

The components of this multifaceted approach, including each dedicated team's specific responsibilities, are discussed below.

### **10.3.1. Data and Safety Monitoring Board**

A DSMB will provide an independent review of the research, interim safety and efficacy data, and progress towards achieving the goals of the study. To enable the CCC to properly manage the trial, the project leadership, and key personnel will jointly work on a DSMB plan early in the process. After the award but before the project begins, CCC will be coordinated with the DCC to develop a detailed monitoring plan. The NIH-appointed DSMB will then approve the plan. The monitoring plan will describe the process for reporting adverse events to the IRB, FDA, and NIH.

**DSMB Administration:** DSMB(s) will monitor safety and performance and review interim trial analyses. At periodic patient-completion milestones, the DSMB will meet to review the data for safety, efficacy, and quality. Investigators and staff involved in the interim analyses will attend open sessions of the DSMB meetings to present analyses and, if needed, respond to questions and directly obtain requests for new analyses or revised presentation formats. The trial leadership will follow the pretrial steps recommended by the NIH's NINDS. The CCC has extensive experience with DSMB preparation and reviews.

Interim safety analyses will be prepared for the external DSMB on a pre-arranged schedule (such as semi-annually or after enrollment of a fixed number of subjects) to evaluate efficacy and safety. Safety measures include: monitoring incidence of symptomatic and asymptomatic intracranial bleeding events (i.e., hemorrhage extension, new hemorrhage, catheter tract hemorrhage) through daily computerized tomography (CT) scans for the first four to five days after enrollment and until day seven (about 24 hours after ICH catheter removal), monitoring the incidence of confirmed and suspected

infection, and in-hospital mortality. Safety events will trigger a “suspend recruitment and review” by the DSMB. The DSMB will then investigate the presumed cause and impact of these events are: 30-day mortality > 60%, a MIS and rt-PA related symptomatic bleeding rate > 25% (events identified within the first 30 days and assessed as occurring during active treatment or during the 72 hours after treatment will be monitored), first week operative death rate > 10%, and a procedure-related infection rate > 15% (over the initial 30 days). If any of these events are attributable to the catheter insertion or manipulation, or to the rt-PA injection at a 95% confidence level, then the study will be suspended for a complete safety and efficacy review. The FDA IND division will be notified according to FDA regulations, part 312.

Prior to DSMB report generation, the CCC will work with the enrolling sites to finalize the case forms, compile the data, conduct all requested analyses, and compile suitable reports, tables and graphs. General rules for this analysis are laid out in the DCC grant. All deaths will be reviewed. The most likely complications from this therapy are increased mortality, rebleeding, and cerebritis. We propose to analyze the safety data in two groups to approximate complications attributable to surgery and to the ongoing drug irrigation. The first consists of bleeding and complications within the first 24 hours after catheter placement. The second consists of bleeding and procedure-related complications in the subsequent six days.

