### 3 STUDY DESIGN

This study is a phase III, randomized, open-label, multicenter evaluation of MIS and ICH lysis with rt-PA versus medical care. The study (n=500) will evaluate the efficacy and safety of MIS plus 1 mg of rt-PA administered every eight hours for up to nine doses as compared to subjects treated with conventional medical management. Outcome assessment will be performed by local certified investigators and adjudicated by central blinded investigators.

Subjects enrolling in this study may also consent to participate in an ancillary study titled *Mechanisms of Tissue Injury in MISTIE III*. This ancillary study offers a tremendous opportunity to leverage clinical trial data to bring novel insights from ICH pathophysiology into the clinical realm, using neuroimaging, genetic and inflammatory markers of disease to provide clinicians with powerful new tools to guide surgical therapy and develop new therapeutic targets. See Appendix 8 for the ancillary study protocol.

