Study centers failing to enroll over 5-7 months will undergo remediation with possible termination. Study centers in this situation may appeal to the CCC. If the study center can present a strong case for extenuating circumstances, then the site will remain in the trial for up to 9 months. At 9 months, study centers will be placed on probation with a final opportunity to enroll or be closed at 12 months.

4.3.5 **Informed consent.** The informed consent document will be used to explain the risks and benefits in simple terms to the patient or authorized representative

before the patient is entered into the study. The informed consent document must contain a statement that the consent is freely given, that the patient/authorized representative is aware of the risks and benefits of entering the study and the patient is free to withdraw from the study at any time. A sample informed consent form for all sites is included in Appendix 1 with an additional HIPAA template for international enrolling centers in Appendix 2.

The Investigator or designee is responsible for obtaining informed consent from each patient or their authorized representative and for obtaining the appropriate signatures and dates on the informed consent document prior to the performance of any protocol procedures and prior to the administration of study drug. Informed consent by an authorized representative of the patient should be obtained according to the clinical judgment of the investigator.

- 4.3.6 **Randomization.** Patients who meet all of the inclusion and exclusion criteria using the above screening procedures and who provide consent will be randomized to conventional medical management or surgery (MIS+rt-PA).

For those subjects randomized to surgery (MIS+rt-PA), the operative procedure should occur as close as possible to the time of randomization. If the surgical procedure is postponed to accommodate scheduling (i.e., it is preferable to wait until 6 am instead of midnight), obtain a CT scan to re-confirm stability of the ICH and re-confirm blood pressure stability prior to beginning the surgical procedure. If either or both are unstable, refer to page 23, Stability CT scan for clot stability and page 27, Cardiovascular management for BP stability.

The first dose of study drug is administered six or more hours after the surgical procedure and only after surgical center review.

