After placement of the catheter and a CT scan to confirm correct placement, a six-hour post-surgical stabilization period is required prior to first injection of rt-PA. Keep the drainage system to drainage for six hours post catheter placement *prior* to first dose of rt-PA. This time is mandated to reduce the possibility of secondary hemorrhage. If new bleeding or bleeding expansion is seen on the post-op CT scan, wait 12 hours and repeat the CT scan. When the bleeding is stable, dosing can be initiated.

If post-operative clot volume is 10 to 15 mL, rt-PA should not be given. The catheter should remain in place and open to drainage for 24-36 hours prior to removal.

**Catheter adjustment/replacement:** Correct catheter placement will be CT-confirmed locally and post-operative measurements will be repeated centrally by the Surgical Center. Catheter adjustments will be made at this time, if necessary. If the hematoma appears larger or the shape is altered on CT scan after the catheter is placed, the catheter may require repositioning and a post-repositioning CT scan to confirm correct placement within the clot as well as stability of clot size. Repositioning is defined as the partial removal or “pull back” of the non-optimally placed catheter. Replacement is defined as removal of the catheter and replacement with a better targeted catheter using the introducer method described above with either the same or a different trajectory of insertion. There is a one-time allowance for a new rigid cannula placement. Soft catheter placements or replacements, usually done through an existing burr hole and always done using a stylet with image guidance, do not count against this limited number of rigid cannula passes. There is no limit to the number of soft catheter placements or replacements as long as stability requirements are met. Occasionally it may be necessary to create a new burr hole/trajectory to access the clot. This will be done only after consultation with the Surgical Center. Repeat CT scan and upload DICOMs of the final catheter placement in the clot into the EDC for Surgical

Center review and approval of catheter location in residual hematoma prior to dosing.

The catheter is then tunneled subcutaneously, connected using sterile technique to a three-way stopcock and then to a closed drainage system. Level the drainage bag to zero.

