**Documentation of dosing.** In addition to documenting each dose in the EDC system, each dose administration should be documented in the Medical Administration Record of the medical record as source documentation. A progress note should also be written in the medical record as source documentation to record the date and time of each dose, the amount of rt-PA administered, the amount of flush administered, the catheter in which the drug was administered (when more than one catheter is in place), the time the catheter was closed and reopened, the ICP (if monitored), systolic blood pressure (SBP), and diastolic blood pressure (DBP) prior to the dose and prior to reopening the catheter, and the name and title of the person who administered the dose.

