14.0. Safety Analyses

14.1. Mortality and Safety Events at 30 Days Post Randomization

The primary safety measures for this study are symptomatic intracranial bleeding, infection, and 30-day mortality. The safety thresholds for these measures have been set as: 30-day mortality >60%, a MIS+rt-PA–related symptomatic bleeding rate >25% (occurring during active treatment or during the 72 hours after treatment will be monitored), first-week operative death rate >10%, and a procedure-related infection rate >15% (over the initial 30 days). Bleeding will be further characterized as during the exposure to dosing of alteplase and the subsequent 72 hours. Comparisons to medical subjects in the same time frame will be made. Total SAEs at 30 and 180 days, as well as summary of AEs and SAEs by MedDRA code and grouped by organ system, will be compared by treatment groups.

Statistical Hypothesis: Early use of MIS+rt-PA for 3 days for the treatment of ICH is as safe as medically managed ICH, measured by rates of procedure-related mortality, rebleeding, and infection within 30 days post-randomization. The null hypothesis is: *Early use of MIS+rt-PA is worse than medical management for a specific safety measure.*

Analysis: The number of SAEs will be tabulated by SAE type post-stroke for the total population as well as by treatment group, with particular emphasis placed on group differences at 30 days post-randomization. Any treatment group differences in SAEs enumerated for interim analyses will remain blinded to investigators associated with this study. Unmasked results (e.g., group A versus B, where the labels "A" and "B" are randomly assigned to the surgical and medically managed groups) will be made available only during the closed sessions of DSMB meetings.

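### The 24-hour cut in the DSMB safety split does not separate surgical from rt-PA complications, because up to three rt-PA doses can precede it

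*Protocol*

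**What the plan says.** Protocol 10.3.1, on preparing DSMB reports, gives the purpose of the split: "We propose to analyze the safety data in two groups to approximate complications attributable to surgery and to the ongoing drug irrigation". It defines the groups by time since catheter placement: "The first consists of bleeding and complications within the first 24 hours after catheter placement", and "The second consists of bleeding and procedure-related complications in the subsequent six days". It makes no provision for events that follow a dose but fall before 24 h, or for surgical subjects who are never dosed.

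The dosing rules are elsewhere. Protocol 5.1.2 states that "a six-hour post-surgical stabilization period is required prior to first injection of rt-PA". Protocol 4.3.6 agrees: "The first dose of study drug is administered six or more hours after the surgical procedure and only after surgical center review". The design section gives "1 mg of rt-PA administered every eight hours for up to nine doses", and 5.1.3 allows two hours either side of each scheduled dose. The schedule of evaluations (6.1) lists rt-PA from Day 1. Protocol 5.1.2 and section 8 also describe surgical subjects in whom dosing is not started because of the clot volume remaining after surgery.

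The SAP does not repeat the 24-hour split. Section 14.1 ties bleeding to dosing: "Bleeding will be further characterized as during the exposure to dosing of alteplase and the subsequent 72 hours".

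**The concern.** The first window stands for surgery and the second for drug irrigation, but the boundary is a fixed time after placement and not the start of drug exposure. A subject dosed early spends much of the surgical window already exposed to rt-PA. A subject never dosed contributes later events to a window that stands for a drug they did not receive. The split therefore errs in both directions for its stated purpose.

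What is at stake is how a DSMB member reads the timing table. Protocol 2.2, reviewing the phase II safety data, acknowledges that bleeding is hard to assign to procedure or drug, so a table offered to help with that question should at least put its boundary where exposure changes. The grouping also departs from SAP 14.1. A bleed at 10 h in a subject first dosed at 6 h is in the first group under 10.3.1 and within alteplase exposure under the SAP.

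**Working it through.** There is no plan figure to reproduce; the check is schedule arithmetic.

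Inputs:
- Boundary: 24 h after catheter placement (Protocol 10.3.1).
- Earliest first dose: 6 h after placement or surgery (Protocol 4.3.6, 5.1.2, 5.1.3).
- Interval: 8 h nominal, taken as 6 to 10 h from the two-hour allowance (Protocol 5.1.3).
- Maximum: nine doses (Protocol section 3).
- First-dose times after 6 h: assumed values, because the documents give no distribution.

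Formulas: dose k falls at t(k) = t(1) + (k − 1) × interval. The share of the first window after drug exposure began is (24 − t(1)) / 24.

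| First dose | Doses before 24 h, 6 h interval | 8 h interval | 10 h interval | Share of window after first dose |
|---|---|---|---|---|
| 6 h | 6, 12, 18 (3) | 6, 14, 22 (3) | 6, 16 (2) | 18/24 = 75% |
| 12 h | 12, 18 (2) | 12, 20 (2) | 12, 22 (2) | 12/24 = 50% |
| 18 h | 18 (1) | 18 (1) | 18 (1) | 6/24 = 25% |
| 24 h | none | none | none | 0/24 = 0% |

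With 6 h intervals and a first dose at 6, 12 or 18 h, a further dose falls exactly at 24 h and is not counted as before the cut. The range is 0 to 3 doses. On the nominal schedule from 6 h, 3 of 9 possible doses (33%) are given inside the surgical window.

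Later first doses are realistic. Dosing waits for Surgical Center review (4.3.6, 5.1.3). Repositioning before dosing brings a new six-hour wait (5.1.3). New bleeding on the post-operative CT brings a 12-hour wait and a repeat scan (5.1.2). The 18 h row corresponds, for example, to 6 h plus a 12 h hold.

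Check of the alternative: if the boundary is each subject's own first-dose time, no dose can fall in the pre-dose period, whatever the schedule.

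**The case against.** The strongest reply is that little depends on this split.

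- **Suspension.** A reader might infer that moving an early post-dose bleed to surgery could hide an rt-PA signal from the suspension rule. The documents do not support that. The bleeding trigger (above 25%) is one rate for procedure and drug together, followed through treatment and the 72 hours after it. The attribution clause in 10.3.1 covers catheter or rt-PA alike, so relabelling a bleed from one to the other leaves it inside the rule. The 24-hour split feeds no threshold or test.
- **Causality.** Relatedness to the procedure and to rt-PA is judged event by event (10.4.2), and cerebral bleeds go to the medical monitor and the safety event committee (10.4.1). The split is not the only route to attribution.
- **Wording.** The protocol proposes an approximation, refers to general rules in a grant that is not among the documents, and leaves a detailed monitoring plan for DSMB approval. The link from first window to surgery and second to drug rests on sentence order. The second group is itself worded around the procedure, and one plus six days matches the seven-day attribution window for the procedure in 10.4.2.
- **SAP.** Section 14.1 already gives a dosing-anchored view of bleeding. It adds a description and does not define exclusive categories, so the two tabulations can coexist.

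All of this limits the consequence; none of it repairs the split. An approximation is reasonable when the exact quantity is missing, but here the protocol requires a progress note "to record the date and time of each dose". SAP 14.1 covers bleeding only, whereas the 10.3.1 grouping also covers other complications. If the windows were not meant to stand for surgery and drug in that order, the text does not say what they stand for.

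**Conclusion.** The concern holds as a defect in one descriptive DSMB tabulation. The 24-hour cut does not do what 10.3.1 says it is for: zero to three rt-PA doses can precede it, between 0% and 75% of the first window can follow the first dose, and never-dosed surgical subjects have later events in the drug window. It also differs from the window in SAP 14.1. The suspension thresholds and event-level causality review are untouched.

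A reader might go further and infer that most bleeds in the first group follow rt-PA, for instance 50% to 75% of them. That needs every first dose to fall between 6 and 12 h and a constant bleeding hazard over the first day. The documents give no first-dose distribution, and the mandated six-hour wait, intended to lower the risk of secondary bleeding, suggests that early hours carry more risk. Nor is a bleed after a dose thereby caused by the drug; it may still be surgical. The number of misplaced events and the number of never-dosed subjects cannot be computed from the documents.

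**What to change.** In Protocol 10.3.1, replace the fixed cut with a table for surgical subjects based on recorded dose times:

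- (i) catheter placement to first rt-PA dose;
- (ii) first dose to 72 h after the last dose, labelled joint procedure-plus-rt-PA exposure, in line with SAP 14.1;
- (iii) later;
- never-dosed surgical subjects in a separate row, not pooled into (i).

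Report time at risk with each count. Classify each bleed by the time of the CT that detected it and of the last clear CT, and flag those whose interval spans the first dose.

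The cost is rewording one paragraph and reprogramming the DSMB table. Dose times and CT times are already recorded (Protocol 5.1.3 and 6.3.9), and no dosing or clinical rule changes.

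Three downsides should be stated with the table. Period lengths vary between subjects, hence the time at risk. Because dosing waits for stability, the pre-dose period and the never-dosed row are selected for early bleeders, so the rates are descriptive and not a causal comparison of surgery with rt-PA. Events not found by imaging may have dates only (10.4.2 describes duration by start and end dates), so some on the day of first dosing may not be classifiable.
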